**Multicentre Randomised Controlled Trial of
Compression Therapy following Endovenous Thermal
Ablation of Varicose Veins**

FULL TITLE

A multicentre randomised controlled trial of compression therapy following endovenous thermal ablation of varicose veins.

SUMMARY

This study will be looking at the effect of compression therapy in patients having endovenous treatment for truncal incompetence of their varicose veins using either radiofrequency ablation (RFA) or endovenous laser therapy (EVLT). Patients will be randomised to either the compression group (group A) or the no compression group (group B).

The pain scores, compliance, quality of life scores, occlusion rate at 6 months as well as the cost effectiveness of each intervention will be assessed.

OBJECTIVES

- Primary Objective

Patient's pain score for the first 10 days post-procedure using the visual analogue scale (VAS)

- Secondary Objective

The secondary objectives would be to compare the two treatment groups with respect to:

- The quality of life scores at baseline, 2 weeks and 6 months using the EQ-5D, AVVQ and CIVIQ scores
- The clinical change using the VCSS at baseline, 2 weeks and 6 months
- The degree of bruising and phlebitis at 2 weeks and 6 months
- The patient compliance with the intervention
- The time taken to return to work and normal activities
- Occlusion rates at 6 months
- Comparison of the cost effectiveness of the intervention

Background

Varicose veins are common and are known to affect approximately one third of the population¹. Chronic venous disease (CVD) has been shown to have a negative impact on the quality of life of patients and treatment of varicose veins has been demonstrated to lead to improvement in the quality of life of patients²⁻⁴. Over the past decade, new endovenous techniques have been introduced and these are felt to be cost-effective, especially, when performed in an outpatient or 'office-based' setting⁵.

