Between December 2006 and February 2008, Bakker and colleagues conducted a prospective randomised controlled trial on the use of compression stockings after endovenous laser ablation of the great saphenous vein¹⁰. One hundred and nine patients were approached with 93 finally randomised to use compression stockings for 2 days (Group A) and 7 days (Group B), respectively. All patients were followed up for 3 months post-treatment and the visual analogue scale (VAS) for pain was recorded at 48 hours, 1 week and 6 weeks. A physical examination and quality of life was assessed at 1 week and 6 weeks. Occlusion rate at the 3 month point was also evaluated. Physical function and vitality was shown to be significantly better in group B at 1 week follow-up, but there was no statistically significant difference at 6 weeks. At 1 week, it was also noted that the VAS score in group B (VAS score 2.0 ± 1.1) was significantly lower than in patients wearing compression stockings for 48 hours (VAS score 3.7 ± 2.1) ($p \leq 0.001$)¹⁰. No significant difference was, however, observed at 6 weeks post-procedure. Limitations of the study include the high drop out of the trial (40 out of the initial 109 approached) and the absence of any phlebectomies or sclerotherapy in the patients.

Elderman et al. carried out a randomised trial to assess the effect of compression stockings after endovenous laser therapy (EVLT) for great saphenous vein incompetence¹¹. Patients' reported pain scores and quality of life scores was evaluated on the day of the procedure, 2-3 days afterwards and 2-6 weeks post-procedure. A total of 111 patients were randomised to stockings (n=55) and no

stockings (n=56). There was a statistically significant difference in the pain scores in favour of the stockings group up to day 7, but this difference was no longer present by week 6. There was also a greater use of analgesia in patients in the no stockings group compared to patients wearing stockings ($p < 0.05$). In addition, patients wearing stockings reported a statistically significantly higher score of satisfaction at 2 days (4.44 vs 4.15) and at 6 weeks (4.59 vs 4.18). The absolute difference was, however, small. Two notable limitations of the study were the high level of drop outs (16 from each group) and the absence of any blinding.

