Patients randomised to group A will be asked to wear compression stockings for 1 week.

Patients randomised to group B and undergoing endothermal ablation only will not be provided with any compression. However, if they receive adjuvant treatment to their tributaries, they will be provided with bandages to wear for 24 hours only, with no further compression afterwards.

At baseline, patients will be asked to fill quality of life questionnaires (EQ-5D, AVVQ and CIVIQ) and will have their clinical scores assessed (CEAP and VCSS). On discharge after their varicose vein intervention, they will then be provided with a diary to record their post-procedural pain every day for 10 days using a validated visual analogue scale (VAS) as well as to record when they return to their normal activities and are back to work. They will also be asked to attend a follow-up in 2 weeks and at 6 months.

Patients' GP will also be sent a letter to inform them of their patient's participation in the study.

Follow-up

Patients will be followed up in the outpatient clinic at 2 weeks and 6 months.

Follow-up at 2 Weeks

At the 2 weeks' follow-up, the diary containing details of the pain scores and how soon patients were able to return to normal activities/work will be collected. In addition, patients will be asked about any bruising or phlebitis they have had in the two weeks after their procedure and how compliant they have been with the compression. They will be examined and the Venous Clinical Severity Score (VCSS) will be recorded. They will also be asked to fill in the EQ-5D, AVVQ and CIVIQ scores.

Follow-up at 6 Months

At the 6 months follow-up, patients will be examined and their VCSS will be recorded. They will also be asked to fill the EQ-5D, AVVQ and the CIVIQ scores. They will have a venous Duplex scan to determine occlusion of the treated vein.

Sample Size and Study Duration

We estimated the sample size needed to observe a difference of at least 10mm in the VAS score, with a standard deviation of 20mm. With power at 90% and 5% significance equivalence, we would need to recruit 174 patients (87 per group).

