Previous studies looking at compression stockings have shown drop out rates close to 37% at 3 months¹⁰. Therefore, if we estimate a drop out rate of about 50% by 6 months, we would need to recruit at least 348 patients. If we recruit at least 7 patients per week, this will be approximately a total of 364 patients that could potentially be randomised over the year. With 6 months follow-up, therefore, the study will be running for 18 months with a target recruitment of 350 patients.

Settings

Two hospital trusts in London will be recruiting patients for the study. These will be the:

1. Imperial College NHS Trust
2. North West London Hospitals NHS Trust

ETHICAL ARRANGEMENTS

Ethical approval will be sought from a Regional Research Ethics Committee as per the National Research Ethics Service. Patients will be screened by [name] (or another research fellow), who is also members of the direct care team, and patients thought eligible will be provided with information material about the trial and varicose veins and its treatments.

They will be invited to attend for their varicose vein procedures another day and will have until then to consider their participation into the trial (more than 24 hours to consider).

On the day of their procedure, they will be asked by [name] (or another research fellow) to confirm their consent by providing a written consent prior to participating in the trial.

The National Health Service (NHS) Trust Research and Development approval will also be sought prior to starting the trial.

DATA HANDLING & DISSEMINATION OF RESULTS

All patient data will be anonymised and stored on a password protected access database under the guidelines of the Data Protection Act 1998. Patient records will be kept on paper in the form of the diary card questionnaires and clinical scoring sheets. These will be kept in a locked filing cabinet at the and stored at the Charing Cross Hospital for 10 years in accordance with the Imperial College Trust Policy.

Data and study findings will be presented locally within the hospital, as well as national and international peer reviewed presentations and peer-reviewed journals.

Criteria for Electively Stopping the Trial or Other Research Prematurely

The trial may be stopped prematurely due to loss of equipoise or any major adverse effect as a result of treatment in any of the treatment arms.

Adverse events

No significant adverse events are expected.

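### Does a 6-month drop-out allowance, supported by a rate among patients approached, leave the recruitment target wrong for a 10-day pain endpoint?

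*Combined protocol and SAP*

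**What the plan says.** The section Sample Size and Study Duration sizes the trial on VAS pain, to detect "a difference of at least 10mm in the VAS score, with a standard deviation of 20mm". It continues "With power at 90% and 5% significance equivalence" and arrives at 174 patients, 87 per group. For losses it first cites a precedent: "Previous studies looking at compression stockings have shown drop out rates close to 37% at 3 months". It then sets its own allowance: "Therefore, if we estimate a drop out rate of about 50% by 6 months, we would need to recruit at least 348 patients". The recruitment target is rounded to 350.

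The Background gives the source of the precedent, an earlier trial of stocking duration. There, "One hundred and nine patients were approached with 93 finally randomised", and a listed limitation is "the high drop out of the trial (40 out of the initial 109 approached"). The Background also describes a second stocking trial, which randomised 111 patients and lost 16 from each group.

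Under Objectives the primary outcome is the patient's "pain score for the first 10 days post-procedure using the visual analogue scale (VAS"). Under Follow-up at 2 Weeks, "the diary containing details of the pain scores and how soon patients were able to return to normal activities/work will be collected". Quality of life, VCSS and vein occlusion at 6 months are secondary, and none has its own sample-size calculation.

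**The concern.** Inflation for drop-out should use the loss expected after randomisation, up to the time the primary endpoint is measured. The plan appears to depart from this twice. A rate among patients approached mixes people who were never randomised with people who were randomised and then lost. And loss by 6 months says little about a diary that is complete at day 10 and handed in at 2 weeks.

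If both points mattered, the trial would recruit many more patients than its primary question needs, the stated power would not describe the trial actually run, and an ethics committee could not see what the extra patients are for. In an unfunded study that spends a year recruiting, the question is fair.

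**Working it through.** **Inputs.** Difference 10 mm, SD 20 mm, power 90%, significance 5%, 174 patients, 50% loss, target 350 (Sample Size and Study Duration). Earlier trial: 109 approached, 93 randomised, 40 dropped out. Second trial: 32 of 111 lost (both Background). Two-sided superiority testing is an assumption, because the protocol attaches the word equivalence to its significance level and states no sidedness.

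**Reproducing 174.** n per arm = 2(1.960 + 1.282)² × (20/10)² = 84.1, so 85; the t-test version gives 85.03, so 86. An equivalence formula (assumed margin 10 mm, true difference 0, one-sided 5%) gives 2 × [20(1.645 + 1.645)/10]² = 86.6, so 87. The plan's 87 is sound on either reading. At 87 per arm, superiority power for 10 mm is 90.6% (t-test).

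**Reproducing 348.** 174/(1 − 0.50) = 348 exactly. The 37% is not used in this step.

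**The precedent.**
- As cited: 40/109 = 36.7%.
- If the 16 not randomised (109 − 93) are among the 40, as the wording suggests but does not say: 24/93 = 25.8%.
- If all 40 were lost after randomisation: 40/93 = 43.0%.
- Second trial: 32/111 = 28.8%.

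**Is 50% extravagant for 6 months?** If loss continued at a constant rate from 3 to 6 months (an assumption), 25.8% would become 1 − (69/93)² = 45%, and 37% would become 1 − 0.63² = 60%. The 50% lies between them.

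**What the primary endpoint needs and what 350 delivers.** Needed = 174/(1 − d), rounded up. Evaluable = 350(1 − d). Power is for 10 mm, two-sided t-test. The documents give no loss rate for a 2-week diary, so 5% and 20% are assumed values.

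| Loss d | Needed for 174 evaluable | Evaluable from 350 | Power |
|---|---|---|---|
| 5% (assumed) | 184 | 332 | 99.5% |
| 20% (assumed) | 218 | 280 | 98.6% |
| 25.8% | 235 | 260 | 98.0% |
| 28.8% | 245 | 249 | 97.6% |
| 37% | 277 | 220 | 95.9% |
| 43.0% | 306 | 199 | 94.0% |
| 50% | 348 | 175 | 90.8% |

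The target of 348 exceeds the primary need by 348 − 306 = 42 to 348 − 235 = 113 patients at 43% to 26% loss, and by 130 to 164 at the assumed 20% to 5%. Power does not fall below 90% at any loss up to 50%.

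**What a smaller target would cost.** If half the patients are lost by 6 months, 350 randomised leaves 175 with 6-month data. A target of 245 leaves about 122, and 218 leaves 109.

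**The case for a change.** The strongest case for a change is that a sample-size section should let a reader see why each patient is needed, and this one does not. The only evidence offered for 50% is a rate with the wrong denominator, the horizon belongs to secondary outcomes, and the protocol never says the surplus is for those outcomes. The second stocking trial, which has a proper denominator, goes unused. Allowing for very heavy loss might also encourage tolerance of missing diaries, which could bias the pain comparison however high the power.

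The denominator and the horizon stand as criticisms of the justification. The rest goes too far. The 50% is labelled as loss by 6 months, so the protocol does not predict that half the pain diaries will be missing. The 90% is the design power at 174 evaluable patients, and exceeding it because fewer patients drop out is not a mismatch. A corrected rate could not be written in as fact either: 26% is an inference, 43% is the other reading, and the second trial's 29% comes from follow-up to 6 weeks, so it would carry the same horizon problem. Bias from missing diaries is a separate matter that no choice of inflation factor would settle.

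**Conclusion.** No change is needed. The cited 37% uses patients approached as its denominator, and a 6-month allowance is applied to a 10-day endpoint without explanation. Both are weaknesses of wording in a justification whose result errs on the safe side. The protocol's arithmetic reproduces, its 90% power is right for the evaluable number it names, and 350 randomised gives about 94% to 98% power for 10 mm at 43% to 26% loss, and 91% at 50%.

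Rewriting the section would leave the target, the analysis and the results as they are. Lowering the target would be a real change, but it would trade away 6-month data on quality of life, clinical severity and occlusion, and it would rest on a 2-week loss rate that the documents do not supply. Keeping 350 is a fair choice.

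This conclusion assumes an SD of 20 mm, a two-sided superiority test, equal allocation and loss of no more than 50% for the pain diary. Under the equivalence reading the direction is the same: 87 per arm meets the 90% requirement if the margin is 10 mm and the true difference is zero, and more evaluable patients only add power.

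### Does planning for 50% drop-out without a written missing-data rule leave the pain comparison unprotected?

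*Combined protocol and SAP*

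**What the plan says.** Under Sample Size and Study Duration, the protocol derives 174 patients (87 per group) from a 10 mm VAS difference, SD 20 mm, 90% power and 5% significance. It then allows for loss: "if we estimate a drop out rate of about 50% by 6 months, we would need to recruit at least 348 patients". The target is 350. The 50% is extrapolated from a rate close to 37% at 3 months in an earlier stocking trial.

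The primary outcome is daily VAS pain over the first 10 days. Under Follow-up at 2 Weeks, "the diary containing details of the pain scores and how soon patients were able to return to normal activities/work will be collected" at that visit. The outcomes that wait for the last visit include "Occlusion rates at 6 months", VCSS and the quality-of-life scores.

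There is no analysis section, and none is referred to elsewhere. The nearest text is under Consent: patients given a treatment other than the protocol's stay in follow-up and analysis. That covers departures from treatment, not absent data. Three features help collection without being handling rules: the exclusion of people unable or unwilling to complete questionnaires, the written 0 to 10 score requested beside each VAS mark (Appendix 10), and the return address on the activity diary (Appendix 9).

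**The concern.** A plan that expects to lose half its patients would normally say who is analysed, what counts as a usable diary, how gaps are filled and how far the result depends on that choice. This one says none of it. Its Background also names drop-out as a weakness of both earlier stocking trials; of one it writes: "Two notable limitations of the study were the high level of drop outs (16 from each group) and the absence of any blinding". No blinding is described here either, and patients know whether they wear a stocking, so loss could depend on both arm and pain.

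Doubling recruitment restores numbers, not comparability. If the patients who return no diary in one arm had more or less pain than those who do, a comparison of returned diaries is biased, and a larger trial estimates that biased difference more precisely. With no rule on paper, the method could also be chosen after the results are known.

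**Working it through.** **1. The plan's own figures.** Inputs from Sample Size and Study Duration: difference 10 mm, SD 20 mm, 90% power, 5% significance (taken as two-sided).

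- n per group = 2 × (1.960 + 1.282)² × 20²/10² = 84.1, so 85 per group (170 in total). The stated 174 is within 3% of this.
- Loss: 174/(1 - 0.5) = 348, an exact match.
- 350 recruited and 50% lost leaves 87.5 per group, with power about 0.91.

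The inflation does what it is meant to do.

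**2. Which loss rate belongs to which outcome.** The 50% is stated for 6 months, and the diary is due at 2 weeks. The documents give no expected diary loss, so a range is needed:

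- 10% and 20% are assumptions.
- 29% is the loss in the second cited trial: (16 + 16)/111 = 28.8%.
- 50% is the plan's 6-month figure.

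The first cited trial lost 40 of 109 approached (36.7%), but only 93 were randomised. Its loss after randomisation is therefore 24/93 = 26% if all 16 who were never randomised are among the 40, and 40/93 = 43% if none are. The Background does not say which, so neither is used.

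**3. Bias if only returned diaries are compared.** Suppose non-returners differ from returners by a gap g in one arm only, with the same loss d in both arms. Then:

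- bias = d × g
- n per group = 350(1 - d)/2
- SE = 20 × √(2/n)
- smallest significant difference = t × SE (two-sided 5%)
- gap needed to create it from no true difference = t × SE/d

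The gap is an assumption; the documents hold no data on it.

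| Loss d | n per group | SE (mm) | Smallest significant difference (mm) | Gap needed (mm) | Bias at g = 10 (mm) | False-positive chance at g = 10 | False-positive chance at g = 5 |
|---|---|---|---|---|---|---|---|
| 10% | 157.5 | 2.25 | 4.43 | 44 | 1.0 | 7% | 6% |
| 20% | 140 | 2.39 | 4.71 | 24 | 2.0 | 13% | 7% |
| 29% | 124.6 | 2.53 | 4.99 | 17 | 2.9 | 20% | 9% |
| 50% | 87.5 | 3.02 | 5.97 | 12 | 5.0 | 38% | 13% |

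The chances come from the noncentral t distribution. The striking entries are in the 50% row, which borrows a 6-month rate for a 2-week outcome. With equal loss and the same gap in both arms, the bias is d × g - d × g = 0 in every row.

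**4. Does doubling recruitment make matters worse?** At 50% loss and a 10 mm one-arm gap, the false-positive chance is 21% with 174 recruited and 38% with 350. If the same bias runs against a true 10 mm difference, power also rises, from 21% to 38%; at 20% loss it rises from 65% to 92%. Doubling increases one error and reduces the other.

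**5. Would a written rule remove the bias?**

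- Imputation from baseline data assumes that missing pain is predictable from what was recorded. It does not remove a gap that depends on unrecorded pain.
- The 2-week questionnaires are completed at the visit where the diary is handed in, so a patient who misses that visit may lack both.
- A sensitivity analysis shifting missing values in one arm by 0 to 20 mm moves the result by at most 0.1 × 20 = 2 mm or 0.2 × 20 = 4 mm at 10% or 20% loss. Both are below the 4.43 and 4.71 mm needed, so it could not overturn an observed difference of zero.

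**6. Six-month outcomes.** Here the 50% does apply. If half the scans are absent and 90% of those seen are occluded (an assumed rate), the overall rate lies between 0.5 × 0.9 = 45% and 45% + 50% = 95%. These limits follow from the counts alone and can be reported whether or not the protocol mentions them.

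**The case for a change.** The strongest case for a change is that the protocol predicts heavy loss, criticises earlier trials for it, and then relies on numbers alone. One paragraph and a log of reasons would cost almost nothing and would fix the method before results by arm are seen. Even the diary's denominator is loose, since the text speaks of 10 days and Appendix 10 has 11 lines, day 0 to day 10. Equal losses per arm, such as the 16 and 16 in the second cited trial, do not exclude bias, because those lost may differ between arms. For the 6-month outcomes the 50% needs no qualification.

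Much of this stands. The rule is absent, pre-specification has value, and wide bounds on 6-month occlusion are a fair description of a trial that loses half its scans. But occlusion is a secondary outcome, and its uncertainty comes from the loss itself, which no handling rule reduces. For the primary outcome, the harm depends on a large gap confined to one arm, which nothing in the documents supports, or on a loss rate stated for a different time.

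**Conclusion.** No change follows. The protocol has no written policy for missing data, as part of a wider absence of any analysis section, but nothing it does state on this point is wrong: 174 and 348 both check, and power holds at about 91% with half the patients lost. There is no stated method that another would improve on. Any analyst of these data must choose how to treat incomplete diaries, and the usual choices are open without altering the trial: all randomised patients in their allocated group, all recorded days used, numbers missing reported by arm, and a sensitivity analysis wide enough for the loss actually seen. Keeping patients in the analysis after a change of treatment, as the Consent section requires, already points that way.

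The size of the primary concern depends on diary loss, which is not stated. At an assumed 10% to 20%, a 10 mm gap in one arm gives 1 to 2 mm of bias and a false-positive chance of 7% to 13%; a significant result from no difference would need a gap of 44 to 24 mm. The 38% figure requires 50% diary loss and a 10 mm gap in one arm only. These figures assume SD 20 mm, equal loss in both arms and a two-sided 5% test. If diary loss proved to be near 50% and uneven in kind between arms, the published comparison should be read with that in mind.

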Adverse Event (AE): any untoward medical occurrence in a patient or clinical study subject.

Serious Adverse Event (SAE): any untoward and unexpected medical occurrence or effect that:

- **Results in death**
- **Is life-threatening** – *refers to an event in which the subject was at risk of death at the time of the event; it does not refer to an event which hypothetically might have caused death if it were more severe*
- **Requires hospitalisation, or prolongation of existing inpatients' hospitalisation**
- **Results in persistent or significant disability or incapacity**
- **Is a congenital anomaly or birth defect**

REPORTING PROCEDURES

All adverse events should be reported.

Depending on the nature of the event the reporting procedures below should be followed.

Any questions concerning adverse event reporting should be directed to the Chief Investigator in the first instance.

Adverse Events (AE)

All such events, whether expected or not, should be recorded.

Serious Adverse Events (SAE)

An SAE form should be completed and faxed to the Chief Investigator within 24 hours.

All SAEs should be reported to the Research Ethical Committee where in the opinion of the Chief Investigator, the event was:

- 'related', ie resulted from the administration of any of the research procedures; and
- 'unexpected', ie an event that is not listed in the protocol as an expected occurrence

Reports of related and unexpected SAEs should be submitted within 15 days of the Chief Investigator becoming aware of the event, using the NRES SAE form for non-IMP studies.

Local investigators should report any SAEs as required by their Local Research Ethics Committee, Sponsor and/or Research & Development Office.

In the event of any harm to participants in the trial, Imperial College holds Public Liability (“negligent harm”) and Clinical Trial (“non-negligent harm”) insurance policies which apply to this trial.

ETHICS APPROVAL

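### The SAE definition requires an event to be unexpected, which conflicts with the reporting section and leaves the 24-hour duty unclear for serious but foreseeable events

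*Combined protocol and SAP*

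**What the plan says.** All of the relevant text is in the protocol's Adverse events section and the Reporting Procedures that follow it.

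- **AE definition:** "any untoward medical occurrence in a patient or clinical study subject". Expectedness plays no part.
- **SAE definition:** "any untoward and unexpected medical occurrence or effect that" meets one of five criteria: death, threat to life, hospital admission or a longer stay, lasting or significant disability, or congenital anomaly. Expectedness is a condition.
- **General rule:** "All adverse events should be reported". No deadline or recipient is given.
- **AE rule:** "All such events, whether expected or not, should be recorded". Again there is no deadline.
- **SAE rule:** "An SAE form should be completed and faxed to the Chief Investigator within 24 hours". This is the only 24-hour duty, and it sits under the SAE heading.
- **Ethics-committee rule:** "All SAEs should be reported to the Research Ethical Committee where in the opinion of the Chief Investigator, the event was" both related and unexpected. Here 'unexpected' is explained as "ie an event that is not listed in the protocol as an expected occurrence". These reports are due within 15 days of the Chief Investigator becoming aware of the event.
- **Expected events:** the protocol lists none. The Adverse events section opens only with the statement "No significant adverse events are expected".

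**The concern.** Seriousness and expectedness are separate questions. Seriousness should decide whether an event is an SAE and so goes quickly to the Chief Investigator. Expectedness should decide, after that, whether the ethics committee must also be told. The reporting section follows this order and gives the expectedness judgement to the Chief Investigator. The definition does not: whoever first classifies the event must judge expectedness before any SAE form is sent.

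What is at stake is prompt and uniform reporting of serious events. Take an admission for deep vein thrombosis after ablation. The protocol has thromboembolism in view: the Background names its prevention among the indications for compression, and current DVT is an exclusion criterion. It does not say whether a thrombosis after treatment counts as expected. Two members of staff could classify the same admission differently, one sending a form within 24 hours and the other entering an AE with no time limit.

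**Working it through.** There is no figure to reproduce; the check is a comparison of the rules.

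**Step 1. What the definition requires.** SAE = untoward AND unexpected AND serious. AE = untoward. A serious event that is not unexpected fails the SAE definition and remains an AE.

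**Step 2. What follows for a serious event under each meaning of 'unexpected'.**

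| Meaning used in the definition | Event | Class | Duty |
|---|---|---|---|
| Ordinary clinical meaning | Not foreseeable | SAE | Form within 24 hours |
| Ordinary clinical meaning | Foreseeable | AE only | Record and report, no deadline |
| Not listed in the protocol, no list (as now) | Any | SAE | Form within 24 hours |
| Not listed in the protocol, list added later | Listed | AE only | Record and report, no deadline |

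No other part of the protocol restores the 24-hour duty in the second and fourth rows.

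**Step 3. Fit with the ethics-committee rule.** That rule selects SAE AND related AND unexpected. Substituting the definition gives (untoward AND unexpected AND serious) AND related AND unexpected.

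- If the word has one meaning throughout, the final condition repeats one already met and selects nothing. The reporting section is written as though expected SAEs exist; the definition says they cannot.
- If the word has its ordinary meaning in the definition and the list-based meaning in the ethics rule, the protocol does not say so. A related, foreseeable, unlisted serious event would then satisfy the ethics test but would not be put to it, because it is not classed as an SAE.

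**Step 4. Effect of removing expectedness from the definition.** SAE = untoward AND serious. All four rows of the table become SAE with a form within 24 hours. The ethics rule becomes untoward AND serious AND related AND unexpected, so each condition does its own work. If the word has one meaning throughout, the set of events going to the ethics committee is the same as before. If it has two, the only additions are the events described in the second bullet of step 3.

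**The case against.** The strongest reply is that the protocol explains 'unexpected' only once, as not listed as expected; that nothing is listed; and that the Adverse events section says no significant events are expected. Reading one word the same way within a short section is natural, and on that reading every serious event is an SAE today. Only two London trusts take part, so there is limited room for practice to diverge.

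Much of this stands. The list-based reading is available, and on it no event is currently excluded. It would therefore be too strong to say that foreseeable serious events are definitely outside SAE reporting. But the explanation is attached to the ethics-committee test alone, and nothing carries it back to the definition. The general statement about significant events is not a rule for classifying an individual event. Even on this reading the definition duplicates the later test, and a future list of expected events would take those events out of SAE reporting without anyone having decided that it should.

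A reader might also infer that the Chief Investigator would never learn of a foreseeable serious event. The text does not support that. All adverse events must be reported, and AEs must be recorded whether expected or not. The general rule names no recipient, so it does not prove that the Chief Investigator sees every event, but the duty to report remains.

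**Conclusion.** The definition conflicts with the reporting section and should be corrected. The conflict itself does not depend on how sites behave. Its practical reach depends on which meaning of 'unexpected' is applied: on the ordinary meaning, a serious but foreseeable event loses the 24-hour deadline and the SAE label; on the list-based meaning, nothing is lost until a list is added. On either reading the event is still recorded and reported.

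Three larger consequences might be inferred, and the documents support none of them.

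- **A distorted SAE table or comparison between arms.** No SAE table or between-arm SAE analysis is described. Bruising and phlebitis, which are named outcomes, are asked about directly at the 2-week visit and do not depend on the SAE definition.
- **A compromised stopping rule.** The stopping criterion refers to a major adverse effect of treatment. It mentions neither SAEs nor SAE forms, and recorded AEs could inform it.
- **A number of missed events.** The documents give no rate of serious events and no basis for the share that would be classified as expected, so no count is offered.

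The primary endpoint, the sample size and the listed secondary outcomes are unaffected. This is a clear drafting fault in a safety rule, with a bounded effect and a cheap remedy.

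**What to change.** Delete 'and unexpected' from the SAE definition, so that any untoward event meeting one of the five seriousness criteria is an SAE and triggers the existing 24-hour form. Keep 'related' and 'unexpected' only as the Chief Investigator's test for ethics-committee reporting, with the list-based explanation already given there. If expected events are listed in future, the list would then affect only that test.

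The cost is a two-word deletion by protocol amendment and possibly a few more SAE forms. If sites had been using the ordinary meaning of 'unexpected', a few more ethics-committee reports might also follow. No treatment, visit, endpoint or sample-size statement changes.
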